5.3 Usual Care

Both the control and intervention groups will continue to receive usual care as part of this study. Patients at the control sites will receive standard of care, and patients at the intervention sites will receive standard of care plus the pharmacist-led intervention. Usual care for Veteran organ transplant recipients across the 10 study sites varies somewhat, but generally includes the following: at most sites, nurse coordinators and/or mid-level practitioners are responsible for general transplant patient oversight, including ensuring laboratory assessments are scheduled/reviewed and medication regimens are accurate and up to date. However, large patient numbers and workload constraints preclude these health care professionals from prospective detailed daily monitoring of patients. If there is non-adherence to laboratory assessments or medications, they are rarely identified concurrently or early after they occur. Thus, medication safety issues that arise usually do not get identified or addressed until they have caused a clinically significant issue, leading to a health care encounter (clinic visit, ER visit, hospitalization). In addition, during this long-term ambulatory phase of care for transplant patients, pharmacists usually act as consultants and are only involved in direct patient care if an issue arises, and the nurse or provider engages the pharmacist for assistance. Within usual follow up care, pharmacists do not conduct routine daily surveillance of all transplant patients. Most transplant patients have multiple physician providers, both within and outside the VA system, providing care and medication management. This includes a primary care physician to manage common comorbidities (hypertension, diabetes, etc.) and a specialist (nephrology, hepatology) to manage allograft function; other specialists, including endocrinologists and cardiologists, are commonly involved with this patient population as well. Thus, care coordination and communication across these providers and health care organizations can often be fragmented. This usual care environment is complex and difficult to navigate, even for patients with high health literacy.^{3,18}

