9.2 Sample Size and Randomization

Based on the projected enrollment numbers, there is ample power to detect a statistically significant difference between the intervention and control groups with regards to the primary aim of hospitalization and ED visit rates. To determine this, we used data from a recent national study conducted between 2009-2012.⁵³ These results demonstrated that the rate of ED visits after transplant was 1.269 per person-year and 48% of those ED visits resulted in hospitalization. We will enroll 10 sites (5 sites for each study arm) and will have a total of just more than 1,600 patients that are roughly split between the intervention and control sites. We used a conservative estimate of an intra-cluster correlation of 0.05 and calculated a sample size of 1,350 to allow us to detect a 25% relative decrease in ED visit and hospitalization rates with 80% power. The 25% relative improvement in rates is a conservative estimate of intervention effect, based on previous pharmacist-led initiatives the investigators have conducted.^{15,16} After allowing for 15% loss to follow up, we require a total of 1,600 to meet study power. We expect to have 1,689 patients based on site estimates. These power calculations were conducted using a two-sided test for counts with Poisson regression adjusting for intra-cluster correlation and with alpha set at 0.05.

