process measures will serve to both assess the dashboard functionality and allow for modification to improve the efficiency of the intervention. The time assessment data will allow us to determine the amount of time and effort implementing this system requires, as it relates to embedding it into normal workflow processes. This information will be important if the dashboard is deemed effective and is disseminated for use to across the VA, as it will allow administrators to accurately assess the required pharmacist time needed for implementation. Finally, we will assess the type and magnitude of the interventions made using this dashboard to ensure study fidelity. The categorization and magnitude of these interventions will be assessed using the Overhage criteria, which is a well-established and validated method used in numerous studies, included several published by the investigators proposing this study.⁵² We will also assess the number of potential immunosuppression safety issues that occur and compare these between the two study arms. To do so, we will use the dashboard to provide monthly measurements of the following: percent of patients with missing laboratory assessments, percent of patients with alarming laboratory values without follow up scheduled, mean adherence to immunosuppression, based on refill timeliness and estimated using the PDC, percent of patients with a significant drug interaction without a immunosuppressant level and percent of patients with hospital discharge or ED visit without follow up scheduled. These will be measured in all patients and compared between the intervention and control groups at monthly intervals.

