10 DATA COLLECTION AND QUALITY ASSURANCE

10.1 Data Collection and Management

There will two general types of data used for this proposal, which includes operational data used for the dashboard system and research data to assess the impact of the intervention on outcomes. Operational data for the dashboard will be captured through querying the national VA CDW operational database using the FRS environment and stored in VISN 7 space already approved and allocated for this project. These data elements include diagnoses, laboratory values, medication regimens, refill histories, provider types and health care encounters (hospitalizations, ER visits), gathered and queried on a daily basis. The pharmacists at intervention sites will access their site-specific dashboard information stored on the server through an end-user permission access link that will restrict which patients are visible to ensure appropriateness of access to the correct PHI.

For the research component of the proposal, data will be captured through the research CDW and housed within the VINCI environment. We will link the VA data to the SRTR registry and CMS claims data. The CDW will provide data to assess outcomes including hospitalizations, ER visits and costs, as well as mortality. CDW data will also be used to assess interventions by querying pharmacists' progress notes. The CMS data will provide non-VA health care utilization, including hospitalizations and ER visits, as well as non-VA cost estimates. The SRTR data will provide all baseline donor, recipient and transplant characteristics as well as clinical outcomes, including acute allograft rejection, graft loss and death. We will also capture pharmacist entered data, which will be their assessments of the dashboard system. We will deploy a web-based data entry system that the intervention pharmacists will use during the first year of the intervention to assess the dashboard functionality. Queries answered by intervention pharmacists will include the number of alerts received, how many were considered clinically relevant/actionable, time to conduct the intervention and general intervention types. This data will be captured through the use of the REDCap system.

After data is cleaned and completely ready for analysis, we will remove identifiers from the final datasets. This will minimize the risk of loss of confidentiality. All data will be stored on the VINCI system and only approved study personnel will have access to this data.

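### The five medication-safety measures are compared between five and five sites with no pre-go-live value, which loses precision and leaves chance gaps in starting practice in the estimate

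*Combined protocol and SAP*

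**What the plan says.** Section 9.3.2 takes five monthly measures from the dashboard: missing laboratory tests, alarming results with no follow-up arranged, mean adherence as proportion of days covered (PDC), interacting drugs without an immunosuppressant level, and discharges or ED visits with no follow-up arranged. It then says: "These will be measured in all patients and compared between the intervention and control groups at monthly intervals". It names no pre-go-live measurement, change from baseline or baseline covariate.

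Other sections do not supply one:

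- Section 9.4 names its mixed model for the utilization outcomes. Its covariates are patient, donor and transplant characteristics; none is a prior value of the outcome or a site-level practice measure.
- The synopsis (Design and Outcomes) mentions adjusting for baseline patient, provider and facility characteristics, but for hospitalization and ER rates.
- Sections 9.3.2 and 9.4 plan pre-study data, 24 months of them, for costs only.
- Sections 4.3 and 9.2.1 stratify randomization on site size only (below 125 versus 125 or more patients).

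On variation between sites, Section 5.3 states: "Usual care for Veteran organ transplant recipients across the 10 study sites varies somewhat". On the data, Section 10.1 says the dashboard queries the national VA data warehouse (CDW) every day: "These data elements include diagnoses, laboratory values, medication regimens, refill histories, provider types and health care encounters (hospitalizations, ER visits), gathered and queried on a" (the sentence closes by giving that frequency).

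**The concern.** These measures largely describe how a site works: whether laboratory tests are ordered and chased, refills are timely, and follow-up is booked. Nothing in the allocation balances starting practice, and patient-level covariates would not capture it. With ten sites, one arm can start ahead simply through the draw, and the month-by-month contrast then shows that gap together with any effect.

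The measures are secondary objectives and feed a planned paper on process measures (Section 14). They are also the main between-arm evidence on mechanism, since the alert and time data are descriptive only (Section 9.4). The team's previous study of laboratory monitoring with this dashboard was an interrupted time series (Section 2.2), so it has already used pre-intervention values of one such measure.

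**Working it through.** **1. The plan's own figure.** The plan gives no power for the five measures. Section 9.2 covers the primary outcome only: "We used a conservative estimate of an intra-cluster correlation of 0.05 and calculated a sample size of 1,350", to "detect a 25% relative decrease in ED visit and hospitalization rates with 80% power".

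- Rates: 1.269 and 0.75 × 1.269 = 0.952 per person-year, over 2 years.
- Patients per arm before clustering: (1.96 + 0.8416)² × (1/1.269 + 1/0.952) / (2 × ln(0.75)²) = 87.2.
- Design effect at 135 per site: 1 + 134 × 0.05 = 7.7.
- Total: 2 × 87.2 × 7.7 ≈ 1,343, against the stated 1,350. With 15% loss, 1,350/0.85 gives 1,589, against 1,600.

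The figure reproduces. The intra-cluster correlation (ICC) of 0.05 is the only between-site variance figure in the plan, so it is borrowed in step 3.

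**2. Chance gap between arms.** With 5 sites per arm, SD of gap = between-site SD × √(2/5). The between-site SD is an assumption.

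| Between-site SD (points) | SD of gap (points) | Chance that gap exceeds 5 points |
|---|---|---|
| 5 | 3.2 | 11% |
| 10 | 6.3 | 43% |
| 15 | 9.5 | 60% |

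**3. Is that range plausible?** Assume a measure at 30% and the ICC of 0.05. The between-site SD is √(0.05 × 0.30 × 0.70) = 10.2 points and the gap SD is 6.5 points. At ICC 0.01 and 0.10 the gap SD is 2.9 and 9.2 points. At ICC 0.05 and 169 patients per site, the standard error of the arm difference is √[0.4 × (0.0105 + 0.95 × 0.21/169)] = 6.8 points. The difference detectable with 80% power on 8 degrees of freedom is 21.9 points.

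**4. Power gain or loss from the site baseline.** Simulated trials of ten sites compare a t test on 8 degrees of freedom with an analysis of covariance on the site's pre-go-live value (7 degrees of freedom). Rho is the correlation between a site's baseline and follow-up values; the plan does not give it.

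| Rho | Adjusted power, if unadjusted is 60% | Adjusted power, if unadjusted is 80% |
|---|---|---|
| 0 | 53% | 73% |
| 0.2 | 55% | 75% |
| 0.3 | 57% | 77% |
| 0.5 | 65% | 84% |
| 0.7 | 80% | 94% |

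Break-even is near rho 0.4.

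**5. What imbalance does to one realised trial.** Use the step 3 setting and let the site effects in the two periods correlate at 0.8. With no patient-level carry-over, the site means then correlate at 169 × 0.05 × 0.8/9.4 = 0.72, where 9.4 = 1 + 168 × 0.05. A 1-SD baseline imbalance carries 0.72 × 6.8 ≈ 4.9 points into the unadjusted estimate. The unadjusted site-level test has 5.0% type I error overall, but 11.6% when the imbalance exceeds 1 SD and 2.0% otherwise. The adjusted test has 4.9% in the imbalanced trials. Power for a 15-point difference is 49% unadjusted and 72% adjusted. If the site effects correlate at only 0.5 (site means 0.45), it is 49% and 51%.

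**The case against.** The strongest reply is that randomization already deals with chance gaps. A reader might infer that the comparison is biased, or that the effect cannot be separated from the starting gap. The documents do not support that. Sites are randomized, so the contrast is unbiased on average, and a valid site-level or mixed-model test includes between-site variation in its standard error (5.0% type I error in step 5). What remains is lost precision and an estimate that is off in the particular trial that happens to be imbalanced.

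A reader might also infer that the plan prescribes an unadjusted test or one that ignores clustering. It does neither: Section 9.3.2 names no model for these measures. Ignoring clustering would be serious, with type I error of about 48% to 52% at ICC 0.05 and 135 to 169 patients per site, so the model should be named. Silence is still not a commitment to that analysis.

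Three practical objections stand in part:

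- **Data.** Section 10.1 lists laboratory values, medications, refills and encounters, but not appointment scheduling. A baseline is well supported for missing laboratory tests, PDC and interactions without a level. It is not shown for the two measures that depend on whether follow-up was scheduled.
- **Cost.** One might assume that a spent degree of freedom costs almost nothing. With ten sites it costs up to about 7 power points when rho is near zero. The size stratum takes a further degree of freedom, leaving 6 after the baseline rather than 7.
- **Stakes.** These are secondary process measures without a sample-size claim.

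**Conclusion.** The omission is real. No section brings a pre-go-live value of the five measures into the between-arm comparison, while costs do get a pre-period. The consequence is loss of precision and exposure of the realised estimate to chance imbalance, not bias on average.

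The size rests on two quantities that the plan does not give: the between-site SD (5 to 15 points assumed) and the site-level correlation between periods. Adjustment gains 4 to 5 power points at a correlation of 0.5 and 14 to 20 at 0.7, and loses about 3 to 7 at 0.3 or below. Stable site practice would favour the higher correlations, but that is a judgement. This is a cheap improvement to secondary outcomes; the primary conclusion is unaffected.

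**What to change.** Add to Sections 9.3.2 and 9.4:

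- Fix one pre-go-live window and compute each measure for all ten sites from the CDW with the code used after go-live. Do this for missing laboratory tests, PDC and interactions without a level. For the two follow-up measures, do it where scheduling status as it stood at the time can be rebuilt, and otherwise state that no baseline is available.
- Name the model: a between-arm comparison that accounts for clustering by site, with the site's pre-go-live value and the size stratum as covariates and small-sample degrees of freedom. Report the adjusted difference as the result for each measure.
- Section 2.2 says the dashboard was already in use at one VISN 7 site and several in VISN 12. If any trial site is among them, which the available text does not show, take its window from before that use or flag its baseline.

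The cost is SAP wording and a retrospective run of the queries, with some rebuilding for the two follow-up measures. The statistical cost is one residual degree of freedom (7 to 6 with the stratum in the model), with the power loss shown above if the correlation turns out low. The covariate should be fixed before between-arm results are seen. Enrolment, intervention and follow-up do not change.

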9.4 Data Analyses

The data analysis will incorporate the intent-to-treat principle; namely, all participants enrolled in the intervention group will be included in the analysis and compared to all of the patients captured within the control group. If a patient dies, has graft loss or moves out of their study site, their data will be censored at that time point. For comparative statistical assessments within the utilization outcomes, the two groups will be compared using a generalized linear mixed models (GLMM) approach.⁵⁴ This approach allows for measurement of participants at different time points, clustering by study site, missing data under the assumption of missing at random (MAR), time varying or invariant covariates, and can also account for the effect of correlated longitudinal measurements within participants. In addition, GLMM accommodates a wide range of distributional assumptions such as dichotomous (e.g. binomial), count (e.g. Poisson), continuous

(e.g. Gaussian), and categorical or ordinal outcomes. For comparing the primary outcome (ED visit and hospitalization rates), we will use GLMM (with appropriate link function) with counts of these events as the outcome variable and intervention group (yes/no) as the primary independent variable. This analysis is equivalent to Poisson regression or negative binomial regression (in the case of over-dispersion), both special cases of GLMM. Additional adjustment covariables will be added to the model in a second set of analyses. Covariates will include patient sociodemographics: age, sex, race, comorbidities (using modified Elixhauser definitions), marital status and education. In these models, donor information (age, sex, race, deceased or living) and transplant characteristics (HLA mismatches, ischemic times, panel reactive antibody levels, time since transplant) will also be included. This will assist in making valid intervention effect estimates after accounting for baseline differences, as there may be patient-level differences between groups. The magnitude of between intervention differences on outcome variables (effect sizes) at each time point will be estimated using appropriate contrasts in the corresponding GLMM models.

We anticipate that some of the count outcomes will exhibit excess zeros (e.g. hospitalizations). If the counts exhibit excess zeros, we will use zero-inflated (ZI) versions of the proposed model (zero inflated Poisson and zero-inflated negative binomial [NB]) to account for the excess zeros with random effects to account for clustering by site.⁵⁵ Typically, Poisson regression is used to model count data where observations are assumed to be independent and the number of cases has variance equal to the mean for each level of the covariates. However, in practice, either the independence or equal mean and variance assumption is often violated, which can lead to over-dispersion (when the variance is greater than the conditional mean). Thus, we consider a NB model that handles the problem of over-dispersion and that does not assume an equal mean and variance assumption. In certain cases, over-dispersion may not be sufficiently modeled via the extra parameter in NB. In this case we will consider including random effects into the NB model. Zero inflated models such as ZINB can be used for modeling the excess zeros. The ZINB model is a mixture of NB model for the count part and a logit model for the excess zeros. The parameters in the ZINB model have conditional or latent class interpretations, which correspond to a susceptible subpopulation at risk for the condition (in our case ED visits/hospitalizations) with counts generated from a NB distribution and a non-susceptible subpopulation that provides the extra or excess zeros. Thus, the ZINB model parameters are not well suited for quantifying the effect of an explanatory variable in the overall mixture population. We will use a marginalized ZINB model to estimate the population mean count directly, allowing straightforward inference for overall covariate effects.⁵⁶ We will use AIC and BIC, which deal with the trade-off between the goodness of fit and complexity of the models, to choose the best fitting model among the different models; further assessment of the goodness of fit for the final model is made via the Pearson goodness of fit statistic. A model with a smaller value of AIC, BIC, and a Pearson statistic close to one is considered a better fit of the data. We will use SAS 9.4, housed within the VINCI environment, to manage the data and fit all the models.

For the cost analysis, we will also utilize multivariable modelling and propensity score

calibration (PSC).⁵⁷ We will assess the effect of the intervention on different sources of cost which include inpatient, outpatient and pharmacy in addition to the total aggregated cost. The cost models will be estimated using log-normal or gamma models (special cases of GLMM) to examine the association of the intervention with cost, adjusting for the aforementioned patient sociodemographics, donor information and transplant characteristics. Cost will be obtained from VINCI CDW and HERC as inpatient, outpatient, pharmacy and total aggregate for two years prior to the study period and for the two years of the intervention. We will also account for non-VA costs through linkage with CMS claims data. We will estimate different models adjusting for the clinical outcomes in order to examine the robustness of the results. GLMM allows for correlation between cost categories as well as for the likely skewed distribution of cost data. The Park test will be performed to check for the appropriate distribution of the cost data and AIC and BIC statistics for goodness of fit. Since, inpatient cost could exhibit a point mass of zero, we will use marginalized two-part models that are appropriate for semi-continuous data to model the relationship between the intervention and inpatient cost.^{58, 59} In general, statistical analyses will use two-sided tests with alpha set at 0.05.

For the assessment of the functionality of the dashboard and the time required to complete the intervention, there will be no comparisons or modeling within this analysis; we will utilize standard descriptive statistics for these measurements, including mean (SD), median (IQR), proportion (%) and 95% confidence interval. Variables assessed for this outcome will be captured through input into the REDCap database by intervention pharmacists during the first year of the intervention. We will compile the total number of alerts the dashboard system generates at each site and assess the proportion of these that were deemed clinical relevant and actionable by the pharmacists. We will also determine the mean/median time required to complete the intervention on a daily basis and estimate the time per 100 patient days. We will conduct these assessments concurrently on a bimonthly basis for the first year of the intervention, which will allow us to modify the dashboard system's reporting thresholds and improve functionality if deemed necessary by the investigational team. We will also assess the overall functionality of the dashboard at the end of the first year to determine composite metrics. Based on our experience with the current system, after an initial bolus effect, we expect the dashboard will produce two to three new alerts per 100 patient days with one to two of these being relevant and actionable. We will utilize 95% confidence intervals actual versus expected rates.

We will handle missing data using several techniques including multiple imputation and maximum likelihood.⁶⁰ Missing data mechanisms will be examined using both univariate and multivariate methods. We will check for missing at random (MAR) by creating a missing indicator for each missing variable and study the predictors of missingness using logistic regression. If any of the fully observed covariates or outcomes becomes significant in the missing data model then we will use methods for MAR if we do not have any reason to believe that the missing data mechanism is not at random. The proposed GLMM models, which are mixed effects models for the longitudinal data analyses, can handle data that are missing at random (MAR) and provide robust estimates. For the cross-sectional data analysis plan, we will use

multiple imputation approaches and for categorical missing data we will use latent class based multiple imputation.^{57,60}

